### Diagram Showing the Process for Preparing A-101 Study Medication

1. The common wart should be cleaned using an alcohol wipe prior to application of A-101 45%.
2. Hold the applicator so that the applicator cap is pointing up.
3. Crush the ampule in the applicator by applying pressure to the center of the barrel of the applicator.
4. Remove the sleeve.
5. Tap the barrel of the applicator to ensure the solution is free of the crushed ampule.
6. Gently remove the cap by twisting while pulling away from the applicator.
7. Express a single drop of A-101 45% so that the tip of the applicator becomes wet.
8. Apply the solution to the common wart in a circular motion.

Aclaris Therapeutics, Inc.

Protocol Number: A-101-WART-302

Amendment 3: Version 5 14 February 2019

## **APPENDIX 2. PWA SITE USER MANUAL**

Aclaris Therapeutics, Inc.

Protocol Number: A-101-WART-302

Amendment 3: Version 5 14 February 2019

## THE PHYSICIAN'S WART ASSESSMENT (PWA)

To Assess Common Warts on the Trunk or  
Extremities

FOR INVESTIGATOR USE ONLY

CONFIDENTIAL PROPERTY OF ACLARIS THERAPEUTICS  
DO NOT COPY OR DISTRIBUTE

## THE PHYSICIAN'S WART ASSESSMENT (PWA)

### To Assess Common Warts on the Trunk or Extremities

#### INTRODUCTION

Aclaris Therapeutics developed the PWA to facilitate and standardize the rating of common warts in clinical research settings.

The purpose of the PWA is to guide the physician's overall global assessment of the target wart in order to determine the: (a) presence/absence of a wart and (b) extent to which the wart is getting better or not. Though the tool will be used for comparative purposes, the physician should only consider the wart RIGHT NOW when making his/her assessment.

The physician will use his or her clinical judgement and the wart size guidelines to rate the wart under observation on a four-point scale.

[figure not shown]
| Grade | Descriptor   |
|-------|--|
| 0     | Clear: No visible wart. No further treatment is indicated.       |
| 1     | Near Clear: A visible wart <3mm in maximal diameter (or length). |
| 2     | A visible wart ≥3mm and <6mm in maximal diameter (or length).    |
| 3     | A visible wart ≥6mm in maximal diameter (or length).             |

The photographic illustrations provided in this guide are examples of each wart severity grade and can be used to help the physician determine the appropriate grading for the wart under evaluation.

In addition, the physician is encouraged to use a ruler or caliper and to feel the wart or skin area to help make his/her determination.

[figure not shown]
**GRADE 0**

**Clear:** No visible wart. No further treatment is indicated.

[figure not shown]
**GRADE 1**

**Near clear:** A visible wart <3mm in maximal diameter (or length).

[figure not shown]
**GRADE 2**

A visible wart  $\geq 3\text{mm}$  and  $<6\text{mm}$  in maximal diameter (or length).

**GRADE 3**

A visible wart  $\geq 6\text{mm}$  in maximal diameter (or length).

FOR INFORMATION ONLY

## LIST OF ABBREVIATIONS AND DEFINITION OF TERMS

Abbreviation	Term
AE	Adverse Event
ANCOVA	Analysis of Covariance
ANOVA	Analysis of Variance
CBC	Complete Blood Count
CMH	Cochran-Mantel-Haenszel
CPH	Cox Proportional Hazards
CRF	Case Report Form
FCS	Fully Conditionally Specified
ID	Identification
ITT	Intent to Treat
LSR	Local Skin Reactions
MedDRA	Medical Dictionary for Regulatory Activities
MI	Multiple Imputation
PHREG	SAS Procedure for Proportional Hazards Regression
PP	Per Protocol
PT	Preferred Term
PWA	Physician's Wart Assessment
SAE	Serious Adverse Event
SAP	Statistical Analysis Plan
SOC	System Organ Class
US	United States

## INTRODUCTION

The purpose of this statistical analysis plan (SAP) is to provide a description of the statistical analyses performed for the Phase 3 protocol, A-101-WART-302, Amendment 2, Version 4 (12Oct2018).

### 1. STUDY OBJECTIVES

#### 1.1 Primary Objective

The primary objective of this study is to evaluate the effectiveness of A-101 45% compared to Vehicle when applied twice weekly to common warts.

#### 1.2 Secondary Objectives

The secondary objectives of this study include:

- Duration of response to A-101 45% compared to Vehicle.
- Onset of action of A-101 45% compared to Vehicle.
- Safety of A-101 45%.

### 2. STUDY DESIGN

This is a phase 3, multicenter, randomized vehicle controlled, double blind parallel group study to evaluate the safety and efficacy of A-101 45% vs Vehicle in subjects with common warts. Investigators will be required to identify at least 1 and up to 6 clearly identifiable common warts for treatment with A-101 study medication. All identified common warts will be treated twice a week for up to 8 weeks (maximum of 16 treatment applications). Subjects will be required to complete a total of 13 study visits. The protocol defined study visits are:

- Visit 1 (Day -13 to 0) screening
- Visit 2 (Day 1)\* randomization; study medication treatment
- Visit 3 (Day 8)\* study medication treatment
- Visit 4 (Day 15)\* study medication treatment
- Visit 5 (Day 22)\* study medication treatment
- Visit 6 (Day 29)\* study medication treatment
- Visit 7 (Day 36)\* study medication treatment
- Visit 8 (Day 43)\* study medication treatment
- Visit 9 (Day 50)\* study medication treatment
- Visit 10 (Day 60) follow up evaluations, no identified Wart retreatment
- Visit 11 (Day 78) follow up evaluations, no identified Wart retreatment
- Visit 12 (Day 106) follow up evaluations, no identified Wart retreatment
- Visit 13 (Day 137) follow up evaluations, no identified Wart retreatment; end of study

\*The second weekly application will be applied by the subject/parent/legal guardian at home (Day 4, 11, 18, 25, 32, 39, 46, and 53).

Approximately 500 subjects will be randomized to one of 2 treatment arms in a 1:1 ratio

at approximately 25 investigational centers in the US. Of the 500 subjects randomized, approximately 100 subjects will be between 1 and 17 years of age.

The study schedule of assessments can be found in Table 1.A.

## Schedule of Assessments

Visit	V1 Screening	V2	V3	V4	V5	V6	V7	V8	V9	V10	V11	V12	V13
Treatment Day	-13 to 0	1	8	15	22	29	36	43	50	60	78	106	137
Treatment Window	N/A	N/A	±1 day	±1 day	±1 day	±1 day	±1 day	±1 day	±1 day	+4 days	±7 days	±7 days	+7 days
Study Procedures													
Informed Consent	▲												
Inclusion Criteria/Exclusion Criteria	▲	▲ 											
Subject Identifier	▲ 												
Medical history/demographics	▲												
Fitzpatrick Skin Type Assessment	▲ 												
Vital Signs	▲ 								▲				▲
Prior Medications/Therapies	▲ 												
Clinical Chemistry and CBC 	▲												▲
Common Wart Identification 	▲												
Physician's Wart Assessment 	▲	▲	▲	▲	▲	▲	▲	▲	▲	▲	▲	▲	▲
Common Wart Dimensions 	▲	▲	▲	▲	▲	▲	▲	▲	▲	▲	▲	▲	▲
Standardized Photography 	▲	▲ 		▲		▲		▲	▲	▲	▲	▲	▲
Subject Randomization			▲ 										
Local Skin Reactions			▲ 	▲ 	▲ 	▲ 	▲ 	▲ 	▲ 	▲	▲	▲	▲
Study Medication Application 			▲		▲	▲	▲	▲	▲	▲			
Study Medication Application at Home 				A-101 Study Medication will be applied at home on Days 4, 11, 18, 25, 32, 39, 46, 53. A window of +1 day is allowed.									
Subject Instructions	▲	▲	▲	▲	▲	▲	▲	▲	▲	▲	▲	▲	▲
Concomitant therapies 		▲	▲	▲	▲	▲	▲	▲	▲	▲	▲	▲	▲
Adverse Events 		▲	▲	▲	▲	▲	▲	▲	▲	▲	▲		

See Footnotes starting on next page.

Subject inclusion/exclusion criteria will be re-assessed prior to randomization during Visit 2.

Investigational sites will assign a unique five-digit subject identifier to each subject at Visit 1. This subject identifier will be used in all study documentation for the duration of the study.

Each subject's skin must be assessed during Visit 1 using the Fitzpatrick Skin Type Assessment.

Vital signs [including temperature, pulse, respiratory rate, blood pressure, height and weight (Visit 1 only)] will be measured by a qualified staff member at Visit 1, Visit 9 and Visit 13.

Prior medications/therapies will be collected for a time-period of 14 days prior to Visit 2.

A complete blood count (including hematocrit, hemoglobin, platelet count, red blood cell count and morphology, white blood cell count and differential (absolute and %) including basophils, eosinophils, lymphocytes, monocytes and neutrophils and a clinical chemistry panel including albumin, alkaline phosphatase, alanine aminotransferase (ALT), aspartate aminotransferase (AST), blood urea nitrogen (BUN), bicarbonate, calcium, chloride, creatinine, glucose, lactate dehydrogenase (LDH), phosphorus, potassium, sodium, total bilirubin, total protein, and uric acid.

The treating investigator will identify at least 1 and up to 6 common warts located on the trunk or extremities that meet the inclusion criteria.

The investigator will use the Physician Wart Assessment (PWA) scale to assess each identified common wart. The investigator must assess the identified common warts prior to application of the study medication at Visit 2-Visit 9. In order to be eligible for randomization at Visit 2, each common wart must have a PWA grade  $\geq 2$ .

The investigator will measure the dimensions (longest axis and thickness of the common wart) at Visit 1 and prior to randomization at Visit 2. The investigator will be required to measure the longest axis of each common wart at Visits 2-13.

At Visits 1, Visit 2, 4, 6, and 9 (prior to study medication application), and Visit 10-13, a qualified investigational center staff member will take a photograph of each identified common wart using the Aclaris supplied camera. All photographs will be sent to a central imaging laboratory.

At a sub-set of investigational sites (up to 3 sites), subjects randomized at these sites will have additional standardized photographs taken of their common warts at the following time-points: V2-10 minutes post application, 1-hour post application and 24 hours post application.

Subjects will be randomized at Visit 2 prior to application of study medication. Investigational study staff will re-confirm subject eligibility prior to randomization.

The investigator and subject will assess each identified common wart for local skin reactions associated with irritation at Visits 2-13. At Visit 2-Visit 9, the investigator and subject will assess each identified common wart for LSRs prior to the application of the study medication.

During in-office visits, subjects 18 years of age and older will apply their A-101 study medication in the presence of the treating physician or a member of the investigational study staff that has been trained on the protocol. Subjects ages 1 to 17 will have their A-101 study medication applied by a parent/legal guardian in front of the treating physician or a member of the investigational study staff during in-office visits. If the identified common wart meets the criteria for re-treatment the lesion will be re-treated at Visits 3-9. Following application of study medication, subjects must NOT wash/submerge the treated wart for at least 6 hours and they must NOT apply any topical products to the treated common warts for at least 6 hours. Parents/legal guardians of children must ensure that the child does not put the treated area in their mouth, or eyes, until completely dry after the application. If the treated area is not completely dry 10 minutes after the application, the area should be blotted dry.

All subjects will receive their second weekly treatment of the A-101 study medication at home on Days 4, 11, 18, 25, 25, 32, 39, 46, 53 as determined by the PWA assessment performed during the in-office visit. Subjects ages 1 to 17 will have their A-101 study medication applied by a parent or legal guardian. All subjects will need to document the application of A-101 study medication in a subject diary. The second weekly treatment will depend on the PWA performed during the in-office visit that week. If the identified common wart meets the criteria for re-treatment during the in-office visit, then the subject/parent/guardian will perform the second weekly treatment at home.

All concomitant therapies including (topical and oral) prescription medications, over the counter medications and natural supplements and non-drug therapies including chiropractic, physical therapy, and energy-based therapy must be documented in the subject CRF. Subjects must not apply any topical products (e.g., moisturizers, sunscreen, etc.) to the identified common wart within 12 hours prior to any study visit.

The reporting period for Serious Adverse Events (SAEs) begins when the subject signs the informed consent and continues through Visit 11. Non-serious clinical adverse events will be collected following the application of the study medication at Visit 2 and through Visit 11. Non-serious adverse events that occur between the time of consent and study medication application will be documented as medical history. All safety reporting (AEs and SAEs) will conclude at Visit 11 (approximately 28 days after last study medication application) except for clinical adverse events related to local skin reactions.

### **3. STATISTICAL METHODS**

The Intent-to-Treat Population (ITT) will be used for primary and secondary efficacy analyses and summaries. The Per-Protocol (PP) population will be used for sensitivity analyses for the primary efficacy analysis and all secondary efficacy analyses included in the hierarchical testing procedure (Figure 1). Subjects will be summarized and analyzed according to randomized treatment group for efficacy. The Safety Population will be used for safety analyses. Subjects will be summarized according to actual treatment received at first application of study medication for safety.

The baseline scores for PWA will be the last non-missing value collected  $\leq$  the date of the first application of double-blind study medication.

For the purpose of analysis, data will be assigned to an analysis visit based on relative study day as defined in Appendix B.

All Data listings will be sorted by randomized treatment group and subject ID.

#### **3.1 Study Populations, Disposition, Baseline Characteristics, Medical History Concomitant Medications, Exposure and Protocol Violations**

##### **3.1.1 Analysis Populations**

The populations used for analyses will be defined as follows:

- Intent-to-Treat Population (ITT): The ITT population includes all randomized subjects.
- Per-Protocol Population (PP): The PP Population includes all subjects who received at least one application of study medication and had no protocol violations as defined in Section 3.1.6.
- Safety Population: The Safety population includes all subjects who received at least one application of study medication.

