### **8.3. Removal of Subjects from Study Therapy**

A subject may be removed from the study therapy for a variety of reasons, including:

- Unacceptable adverse event
- Subject unwilling or refusal to continue with the protocol defined study visits and/or consent withdrawal for study participation
- Change in compliance with an inclusion/exclusion criteria
- Use of a prohibited medication (through Visit 13)
- General or specific changes in the subject's condition that render the subject unacceptable for further treatment in this study in the judgement of the investigator.

If a subject is to be withdrawn from the study, the Aclaris Therapeutics, Inc. CRA or designee must be informed within 24 hours of the decision to remove the subject from the study.

The study may be discontinued at the discretion of Aclaris Therapeutics, Inc. Some examples of reasons for discontinuation are the occurrence of the following:

- Increased frequency, severity or duration of known AEs
- Medical, regulatory or ethical reasons affecting the continued performance of the study
- Difficulties in the recruitment of subjects

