### **15.2. Analysis of Populations**

The populations used for analyses will be defined as follows:

- Intent-to-Treat Population (ITT): The ITT population includes all randomized subjects.
- Per-Protocol Population (PP): The PP Population includes all subjects who received at least one application of study medication and have no major protocol violations.
- Safety Population: The Safety population includes all subjects who received at least one application of study medication.

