### **16.2. Protocol Violations**

A **protocol violation** is defined as any divergence from the protocol-specific inclusion/exclusion criteria, subject is administered a prohibited medication, and/or GCP guidelines. Protocol violations will be identified and recorded, by study center personnel, on the CRF.

As a matter of policy, sponsor/CRO will not grant **exceptions** to protocol-specific entry criteria to allow patients to enter a study. If under extraordinary circumstances such action is considered ethically, medically, and scientifically justified for a particular patient, prior approval from sponsor/CRO and the responsible IRB/IEC, in accordance with the Sponsor/CROs Standard Operating Procedure (SOP), is required before the patient will be allowed to enter the study. If investigative center personnel learn that a patient who did not meet protocol eligibility criteria was entered in a study (a protocol violation), they must immediately inform sponsor/CRO. Such subjects will be discontinued from the study, except in a rare instance following review and written approval by sponsor/CRO and the responsible IRB/IEC, according to the applicable SOP.

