### **3.1.5 Protocol Violations**

[figure not shown]
Protocol violations will be identified prior to database lock to measure adherence to key aspects the protocol (see section 16.2 of the protocol for full definitions). Specific data fields that will be examined to identify protocol violations include entrance inclusion/exclusion criteria and prohibited prior and concomitant medications as well as all deviations identified by the investigator. All protocol violations will be listed by patient number and summarized (n and percent) by randomized treatment group.

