### 3.2.2 Sensitivity Analyses for the Primary Endpoint

The first sensitivity analysis for the primary endpoint will be an analysis based upon the PP population. This analysis will use the same CMH model described for the primary analysis.

A second sensitivity analysis will be conducted for the primary endpoint using the same CMH model for the ITT population that includes the imputation of missing PWA data using a fully conditionally specified (FCS) regression-based Multiple Imputation (MI) procedure. This regression-based MI will be conducted on the worst (maximum) PWA score for all treated warts at a given visit for each subject. The utilization of the FCS methodology accounts for the correlation within a subject and models mean changes over time in the maximum PWA score. For each subject, only data selected as representative of an analysis visit (i.e. within the defined relative day range and closest to the “target”) as documented in Appendix B are included in the imputation process. The imputed data will be in the form of the maximum PWA score and will be rounded to an integer and bounded by 0 below and 3 above. All imputed maximum PWA scores that are assigned a 0 will correspond to complete clearance of all warts at that visit. The complete clearance at visit 10 using this MI data will be analyzed using the same CMH model described for

the primary analysis. Results from the CMH on the MI data will then be summarized using the Wilson-Hilferty transformation to obtain the sensitivity results primary efficacy endpoint. The SAS syntax used to perform the MI and the MI summary is shown in Appendix A

To assess the impact of missing data imputation on primary analysis results a tipping point analysis will be conducted. This analysis will shift the treatment coefficient in the regression model used in the MI procedure to impose a worse mean maximum PWA for the A-101 45% arm and a better mean maximum PWA for the vehicle arm. The shifts will be from 0 to 3 in increments of 0.5 for the A-101 45% arm and from 0 to -3 in increments of 0.5 for the vehicle arm. Apart from these tipping point shifts, the analysis will follow the same methodology described for the MI procedure. The odds ratio and CMH Chi-square P-value are provided for each of the  $7 \times 7 = 49$  shift combinations for the two arms.

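### One per-protocol set with no cut-off at Visit 10 lets later violations remove subjects from the Day 60 per-protocol analyses; the direction of any bias is undetermined

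*SAP*

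**What the plan says.** SAP 3.1.1 states: "The PP Population includes all subjects who received at least one application of study medication and had no protocol violations". For the definition of a violation it points to a section that is not there ("had no protocol violations as defined in Section 3.1.6"). The SAP's table of contents ends that series at 3.1.5, which is the section on protocol violations, so the reference is probably a numbering slip. Protocol 15.2 is narrower: subjects who "received at least one application of study medication and have no major protocol violations". Neither document defines a major violation or gives a date limit.

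SAP 3.1.5 states "Protocol violations will be identified prior to database lock". It draws them from the entry criteria, from prohibited prior and concomitant medications, and from every deviation the investigator identifies. Protocol 16.2 counts as a violation that a "subject is administered a prohibited medication". Protocol 11.3 bars other treatments of the identified warts (over-the-counter products, cantharidin, liquid nitrogen and others) for the whole study, and Protocol 11.2 tracks concomitant therapy until discharge.

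The set is then used at two different times. SAP 3.2.2 says "The first sensitivity analysis for the primary endpoint will be an analysis based upon the PP population", with the same CMH model at Visit 10. SAP 3.2.5 uses it for the Visit 10 single-wart endpoint. SAP 3.2.3 and 3.2.4 use it for the two Visit 13 endpoints.

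**The concern.** Visit 13 falls 77 days after Visit 10 (Day 137 − Day 60). A violation in that interval cannot have affected the Day 60 PWA, yet it decides whether the subject counts in the Day 60 PP analysis.

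Nor is the exclusion likely to be neutral. The last home application is scheduled for Day 53, so a subject with remaining warts at Visit 10 faces 11 weeks without study treatment. The prohibited therapies are those used on the identified warts. Recurrence apart, a subject who is clear has nothing to treat, and a subject who is not clear does. Membership of the Day 60 PP set can therefore depend on the Day 60 outcome.

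At stake is the usefulness of the first-listed sensitivity analysis of the primary endpoint. SAP 3.6 gives its purpose as testing sensitivity to major violations. If its result also moves with behaviour after the endpoint, a difference from ITT, or agreement with it, is hard to interpret.

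**Working it through.** **Inputs from the documents.** About 500 subjects randomised 1:1 (250 per arm); a subject-level advantage of at least 11 points; stated power above 90%; two-sided alpha 0.05 (SAP 2, 3.2.1, 3.5). The effect measure is the Mantel-Haenszel odds ratio (SAP 3.2.1).

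**Assumptions.** The documents give neither responder rates by arm nor the frequency of violations after Visit 10. I take vehicle rates of 5% and 9%, each with 11 points added for A-101. I let q be the share of Visit 10 non-clearers in an arm who are excluded for a later violation, with q from 5% to 30%, and assume at first that no clearer is excluded.

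**Step 1: the plan's power.** Power = Φ{[Δ√n − 1.96√(2p̄(1−p̄))] / √[pA(1−pA) + pV(1−pV)]}. For 16% v 5%, p̄ = 0.105 and the argument is (0.11×15.81 − 1.96×0.4335)/0.4265 = 2.09, so power is 98.1%. It is 94.0% at vehicle 9%, 90.2% at 12% and 86.4% at 15%. The stated figure reproduces for vehicle rates up to 12%, before any allowance for dropout. The assumed rates are thus compatible with the plan. The 97% simulation figure cannot be rerun, because the Phase 2 data are not given.

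**Step 2: effect of the exclusion.** Within an arm, p_PP = p / [p + (1−p)(1−q)]. The odds of clearance are multiplied by 1/(1−q), so

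OR_PP = OR × (1−q_vehicle)/(1−q_active).

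Example with q = 10% in both arms: A-101 0.16/(0.16 + 0.84×0.90) = 0.1747; vehicle 0.05/(0.05 + 0.95×0.90) = 0.0552; difference 11.9 points. The odds ratio is (0.16/0.84)/(0.05/0.95) = 3.62, multiplied by 0.90/0.90, so it does not change.

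| q A-101 / vehicle | PP rates from 16% v 5% | Difference | OR | Difference from 20% v 9% | OR |
|---|---|---|---|---|---|
| 0 / 0 | 16.0 v 5.0 | 11.0 | 3.62 | 11.0 | 2.53 |
| 5% / 5% | 16.7 v 5.2 | 11.5 | 3.62 | 11.4 | 2.53 |
| 10% / 10% | 17.5 v 5.5 | 11.9 | 3.62 | 11.8 | 2.53 |
| 20% / 20% | 19.2 v 6.2 | 13.1 | 3.62 | 12.8 | 2.53 |
| 30% / 30% | 21.4 v 7.0 | 14.4 | 3.62 | 13.9 | 2.53 |
| 10% / 20% | 17.5 v 6.2 | 11.3 | 3.22 | 10.7 | 2.25 |
| 20% / 10% | 19.2 v 5.5 | 13.7 | 4.07 | 13.9 | 2.84 |

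Differences are in points and were taken before rounding. At 16% v 5%, equal shares of 5%, 10% and 20% exclude about 22, 45 and 90 subjects; for 10%, 250×0.84×0.10 + 250×0.95×0.10 = 44.75.

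**Step 3: no true effect.** Equal exclusion gives an odds ratio of 1.00. Unequal exclusion gives 0.80/0.90 = 0.889 (vehicle loses more) or 0.90/0.80 = 1.125 (A-101 loses more).

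**Step 4: power under equal exclusion of 5% to 30%.** It stays at 97.9% to 98.1% (against 98.1%) at vehicle 5%, and at 92.8% to 93.8% (against 94.0%) at vehicle 9%.

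**Step 5: stratified check.** I simulated four wart-count strata, 4,000 runs per scenario. Assumed stratum shares were 35/25/15/25%, with A-101 rates 26/16/10/5% and vehicle rates 10/5/3/1.5%. The median Mantel-Haenszel odds ratio was 3.36 with no exclusion, 3.35 at 10%/10%, 2.99 at 10% A-101 / 20% vehicle, and 3.80 at 20% A-101 / 10% vehicle. The closed form holds under stratification.

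**Step 6: if clearers are excluded too.** With a share s of clearers excluded in an arm, that arm's odds are multiplied by (1−s)/(1−q). When s = q, that arm's rate does not move. The problem arises only when later violations are related to the Visit 10 result.

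**The case against.** A reader might infer that the rule inflates the PP effect and so lets the PP analysis confirm the primary result through selection. The documents do not support that. For the planned odds ratio, equal exclusion changes nothing, and power is flat or slightly lower. Inflation needs A-101 non-clearers to be excluded more often than vehicle non-clearers, and nothing in the documents points that way. If vehicle non-clearers seek other treatment more often, the odds ratio shrinks. The widening of the risk difference under equal exclusion is real, but SAP 3.2.1 does not specify a risk difference as the effect measure. This part of the objection stands.

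It can also be said that only major violations were meant, as in Protocol 15.2 and SAP 3.6, and that a late violation might not be judged major for Day 60. That reading is possible, but the term is undefined and the SAP's own definition omits it, so nothing written prevents the exclusion. Protocol 8.3 refers to prohibited medication up to Visit 13, but only among reasons for removing a subject from study therapy. It is not a PP rule and I do not rely on it.

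Finally, PP carries no alpha. The primary analysis is ITT with missing data counted as not clear, and multiple imputation, a 49-combination tipping-point grid and a site-stratified analysis are also planned. This is correct and limits the weight of the point.

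**Conclusion.** The defect is in the PP definition: membership for a Day 60 endpoint can be decided by events in the following 77 days that are plausibly driven by the Day 60 result. Excluding non-clearers raises the PP clearance rates in both arms. Beyond that the documents do not fix a direction. In the scenarios with 20% exclusion in one arm and 10% in the other, the odds ratio moves by a factor of 0.889 or 1.125.

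These sizes rest on assumed responder rates, assumed exclusion shares and, in the table, no exclusion of clearers. The structural point needs none of them, only a relation between later violations and clearance at Visit 10. The ITT primary analysis and its conclusion are untouched. This is an inexpensive repair to a sensitivity analysis, not a threat to the trial's main result.

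**What to change.** In SAP 3.1.1, define two sets.

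- PP-V10 excludes subjects with entry violations or violations dated on or before the Visit 10 PWA. Use it for the primary and single-wart endpoints.
- PP-V13 applies the same rule through the Visit 13 PWA. Use it for the two Visit 13 endpoints.

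The SAP should also say which cut-off date applies when the PWA is missing, for instance the last day of the Appendix B window for Visit 10 (Day 69). Correct the reference to Section 3.1.6. Reconcile the SAP's exclusion for any violation with the protocol's exclusion for major ones, and define the term if it is kept.

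SAP 3.6 records a correction made after unblinding, so a redefined flag should not replace the specified analysis at this stage. Report PP-V10 as a labelled supplementary analysis beside the PP analysis as now written.

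I would not extend the change to censoring PP time to clearance at the first violation. That would tie censoring to treatment-seeking, which is itself likely to be related to not being clear.

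The cost is a short edit to the definition, a date condition on the PP flag and one extra run for each of the two Visit 10 endpoints. No new data collection is proposed, but violation dates must be available for the flag.
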